## 2.3. Analysis Populations

The analysis populations are described in Table 3.

Population	Description
Randomized	All randomized patients who sign informed consent.
Safety	All randomized patients who take at least 1 dose of double-blind study treatment. In the event of a treatment error, patients will be analyzed according to the treatment they actually received.
Intent-to-Treat	All randomized patients who take at least 1 dose of double-blind study treatment and
(ITT)	have at least one post-baseline efficacy assessment. In the event of a treatment error, patients will be analyzed according to the treatment to which they were randomized.
Evaluable	All patients in the Intent-to-Treat population who complete at least Visit 5 (Week 4) with NPL afficaev scores. Specifically, patients with a diagnosis of psychosis must
	have at least one psychosis sub-scale score at Visit 5 or later and patients with a
	diagnosis of agitation/aggression must have at least one agitation/aggression sub-scale score at Visit 5 or later.

**Table 3. Analysis Populations** 

# 2.4. Treatment Groups

The primary analyses will be performed with patients grouped by treatment arm (i.e. MP-101 or placebo) regardless of their final dose level.

Patients will be randomized to the MP-101 or placebo arm at Visit 2 (Week 0). Patients in the MP-101 arm will begin dosing at 20 mg once daily (QD) of study drug. If in the opinion of the investigator the patient cannot tolerate the initial 20-mg QD dose of study drug (administered for the first week of dosing and assessed at or before Visit 3 [Week 1]), the patient will be discontinued from the study. Study drug intolerance will be determined by the investigator and includes treatment-emergent adverse events (TEAEs) of special interest identified from prior studies, e.g. dizziness, nausea, and vomiting.

At Visit 3 (Week 1), the dose of MP-101 (or equivalent placebo) will be increased to 40 mg. If intolerance is reported at a dose of 40 mg between Visit 3 (Week 1) and Visit 4 (Week 2), the patient will be discontinued from the study.

At Visit 4 (Week 2), the dose of MP-101 (or equivalent placebo) will be increased to 60 mg. If intolerance is reported at a dose of 60 mg between Visits 4 (Week 2) and Visit 5 (Week 4), the patient will be asked to return for an unscheduled visit for down-titration to 40 mg. Patients down-titrated to 40 mg prior to Visit 5 (Week 4) will remain at this dose for the remainder of the study.

At Visit 5 (Week 4), the dose of MP-101 (or equivalent placebo) will be maintained at 60 mg. If intolerance is reported at a dose of 60 mg at Visit 5 (Week 4), the patient will be down-titrated to 40 mg and will remain at this dose for the remainder of the study. If intolerance is reported at a dose of either 40 mg or 60 mg beyond Visit 5 (Week 4) the patient will be discontinued from the study.

## 2.5. Definition of Baseline Assessments

Day 0 (Week 0) is defined in this study as the day of Visit 2. The last assessment made before the first dose of study drug will be defined as the Baseline assessment. This should include all assessments made on or before Day 0. Adverse events that occurred on Day 0 will be assumed to be treatment-emergent, unless the eCRF records that the event started prior to the first dose of study drug.

## 2.6. Definition of Study Visit

Patient data will be analyzed according to the nominal visit collected in the eCRF. Unscheduled visits at which safety data is collected (e.g. labs and ECGs) may result in clinically significant findings or withdrawal, which will be included in adverse event and/or disposition summaries.

## 2.7. Handling of Dropouts and Missing Data

#### Dates

Imputation of missing or partial dates is not expected, but if a complete date is required for calculations, the following algorithms will be applied:

- For the start date:
  - If year, month, and day are missing then use the minimum of the patient's first visit date or the consent date.
  - If either only month or month and day are missing then use January 1.
  - If only day is missing, impute the first day of the month.
- For the end date:
  - If year, month, and day are missing then use the patient's last visit date.
  - If either only month or month and day are missing then use December 31.
  - If only day is missing then use the last day of the month.
  - Do not expand the record past the patient's last visit.

The original missing or partial date, the imputed complete date, and the indicator variable that indicates which dates were imputed will be retained in the database.

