#### **Treatment-Emergent Adverse Events**

Treatment-emergent adverse events (TEAE) include all adverse events that emerge or worsen after taking the first dose of study drug. TEAEs will be summarized for each treatment group by SOC and PT, and by PT in order of decreasing frequency of MP-101 preferred term.

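### For adverse events with a partial or missing start date, SAP 2.7 imputes the earliest possible date with no floor at first dose, so early on-treatment events can be classed as pre-treatment (minor)

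*SAP*

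**What the plan says.** SAP 2.7 (Dates) has one start-date rule for all record types, in three tiers:

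- Day missing: "If only day is missing, impute the first day of the month".
- Month missing, with or without the day: "If either only month or month and day are missing then use January 1".
- Nothing recorded: "If year, month, and day are missing then use the minimum of the patient's first visit date or the consent date".

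The rule is introduced as a contingency: "Imputation of missing or partial dates is not expected, but if a complete date is required for calculations", the algorithm applies. An audit trail is kept: "The original missing or partial date, the imputed complete date, and the indicator variable" stay in the database. Imputed end dates are capped at the patient's last visit. Imputed start dates have no matching lower bound at first dose.

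SAP 6.2 says that TEAEs "include all adverse events that emerge or worsen after taking the first dose of study drug". Its subsections on serious events, deaths, discontinuations, related events, maximal severity, common non-serious events and events of special interest are all built on TEAEs. The one stated default is in SAP 2.5: "Adverse events that occurred on Day 0 will be assumed to be treatment-emergent", unless the eCRF records an earlier start.

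**The concern.** Each tier picks the earliest value that the known parts of the date allow. Whether an event is a TEAE depends on where its onset lies relative to first dose. If the imputed date is used for that comparison, an event that began shortly after dosing, in the same calendar month, falls before it. The error runs one way only: on-treatment onsets can move to pre-treatment, never the reverse.

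TEAEs are a stated secondary endpoint. Protocol Section 3 reports that in the multiple-dose study vomiting was mostly a first-dose effect and nausea tended to occur in the first 3 days. Both are special-interest categories in SAP 6.2. The first days of dosing are where the rule misplaces the largest share of partly dated events. The interim safety review (SAP 3), after about 20 patients complete Week 4, uses a subset of the same displays.

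**Working it through.** The plan gives no figure to reproduce. The check applies the three tiers to known on-treatment onsets and counts how often the imputed date falls before first dose.

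**Inputs**
- The three tiers: SAP 2.7.
- Treatment of 10 weeks, Day 0 being the day of Visit 2: Protocol 7.1, SAP 2.5.
- Consent at Visit 1, 1 to 35 days before randomization: Protocol Section 2.
- Assumptions, not in the documents: first doses are equally likely on every day of a 365-day year, and onsets are spread evenly within each window.

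**Day missing.** Let the month of first dose have L days and let onset be k days after first dose. The imputed date precedes first dose only if onset is in the same month and first dose was not on the 1st. That holds for L - k - 1 of the L possible dosing days (none if this is negative). Summed over 12 months, for k up to 27:

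share(k) = [365 - 12(k + 1)] / 365

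- Days 0-3: the mean of k + 1 is 2.5, so the share is 1 - 30/365 = 0.918.
- Days 1-14: the mean of k + 1 is 8.5, so the share is 1 - 102/365 = 0.721.
- Days 1-70: a month of length L contributes (L - 1)(L - 2)/2 over all k from 1. That is 435 for 31 days, 406 for 30 and 351 for 28. The total is 7 × 435 + 4 × 406 + 351 = 5,020, and 5,020 / (365 × 70) = 0.196.

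**Month and day missing.** The imputed date precedes first dose if onset is in the same year and first dose was not on 1 January: share(k) = [365 - (k + 1)] / 365.

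- Days 0-3: 1 - 2.5/365 = 0.993.
- Days 1-14: 1 - 8.5/365 = 0.977.
- Days 1-70: 1 - 36.5/365 = 0.900.

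**Whole date missing.** The imputed date is no later than consent, which precedes first dose, so the share is 1.

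A day-by-day enumeration over 730 consecutive first-dose dates gives the same results.

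| Onset window | Day missing | Month and day missing | All missing |
|---|---|---|---|
| Days 0-3 | 91.8% | 99.3% | 100% |
| Days 1-14 | 72.1% | 97.7% | 100% |
| Days 1-70 | 19.6% | 90.0% | 100% |

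**Examples.** With first dose on 15 June, an onset on 17 June with the day missing becomes 1 June, which is pre-dose. An onset on 10 July becomes 1 July and stays treatment-emergent.

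**From conditional to overall.** If a fraction f of events in a window has such a date, the share of that window's events lost is f times the table entry. The documents do not give f. The product runs from 0 at f = 0 to the table entry at f = 1, and the SAP's own expectation puts f near the bottom.

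**After the fix.** The imputed date is the later of the first-dose date and another date, so it cannot precede first dose. The share falls to 0%, provided the known date parts are correct and no end date or eCRF entry wrongly indicates earlier onset.

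**The case against.** A reader might infer that the date rule removes on-treatment events from the TEAE tables in general. It does not. Only records with a missing date part are touched, and the SAP does not expect them. With only the day missing, about 80% of Days 1-70 onsets stay treatment-emergent. Protocol Section 3 also says that dizziness, the third special-interest category, tended to be reported later, where the day rule misplaces least.

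The link to TEAE status is inferred. No sentence says that the flag uses the imputed date, and SAP 6.2 gives no date algorithm. SAP 2.5 implies that the eCRF can record an onset before first dose, which may settle some cases. A pre-existing event that worsens after dosing still qualifies.

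Conduct also limits the problem. Adverse events are assessed at every contact, with target gaps of at most two weeks. Queries are resolved before the randomization schedule is released (SAP 2.2), and SAEs are reported within 24 hours (Protocol 9.2.1). Year-only or blank onset dates should therefore be rare. Protocol 10.3.4.1 says that symptoms from before enrollment will be distinguished from new or worsened ones. No statistical testing of adverse events is planned (SAP 6.2).

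All of this stands, and it limits the size of the point. It does not remove it. Beyond Day 0, the SAP offers no other way to classify a partly dated event. The Protocol 10.3.4.1 sentence states an aim without saying how to handle an unknown date. The retained flag lets someone find the affected records but does not correct the tables.

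Nor does SAP 2.5 contradict SAP 2.7, as might be inferred. The first covers events known to have occurred on Day 0, the second covers unknown dates. They lean in different directions but can both be followed.

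**Conclusion.** The point holds in conditional form and is minor. For an adverse event whose partial or missing start date allows onset on or after first dose, the SAP imputes the earliest date and has no default to treatment-emergent. If the TEAE flag is derived from that date, early on-treatment events are lost from the TEAE summaries, which is anti-conservative for safety.

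The percentages rest on the even-calendar assumption and apply only to events with such dates, where the eCRF does not settle the timing. It would be wrong to read 72% or 92% as the proportion of early TEAEs lost. The documents do not give the number of affected events, which may be small or zero.

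**What to change.** Add to SAP 2.7: for adverse events whose known date parts allow onset on or after first dose, the start date is imputed as the later of the first-dose date and the earliest compatible date, and the event is treated as treatment-emergent, unless its end date or an eCRF entry shows onset before first dose. Keep the current rule for other date types. This agrees with the Day 0 default in SAP 2.5.

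The cost is one sentence and a few lines of code. The downside is that a few vaguely dated pre-dose events, mainly from the screening interval of up to 35 days, may be counted as TEAEs. That is the conservative direction for safety.

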#### **NPI Response**

Patients whose response to treatment cannot be determined due to missing data (including early withdrawal) will be considered non-responders.

#### 2.8. Adjustment for Multiplicity

There are no planned adjustments for multiple efficacy endpoints or analyses.

#### 2.9. Adjustment for Multiple Centers

Differences between study centers will be not be incorporated into the statistical analyses for this study. There are no plans to analyze data within centers.

#### 2.10. Adjustment for Covariates

Where possible, analyses will adjust for the baseline value of the endpoint and by the four baseline randomization strata, i.e.:

- MMSE < 16, eGFR < 60
- MMSE < 16, eGFR  $\ge$  60
- MMSE  $\geq$  16, eGFR < 60
- MMSE  $\geq$  16, eGFR  $\geq$  60

## 2.11. Subgroup Analyses

Subgroup analyses based on diagnosis (i.e. Psychosis and Agitation/aggression) at baseline will be performed for the NPI response rate. Other subgroup analyses may be performed. For purposes of analysis, a patient's baseline NPI scores will be used for diagnosis.

Specifically, a patient will be included in the Psychosis subgroup if at least ONE of the following is true at baseline:

- NPI score of  $\geq$  4 on either delusions or hallucinations individual items
- NPI score of  $\geq 6$  on the Psychosis Subscale (combined delusions and hallucinations)

A patient will be included in the Agitation/aggression subgroup if the following is true at baseline:

• NPI score of  $\geq$  4 on agitation/aggression domain

A patient can be in both subgroups.

# 2.12. Coding of Concomitant Medications and Adverse Events

Adverse events (AEs) will be coded using the Medical Dictionary for Regulatory Activities (MedDRA), and concomitant medications will be coded using the World Health Organization Drug Dictionary (WHODD). The versions of the dictionaries used for reporting will be provided in the CSR.

## **2.13.** Computation of Questionnaire Scores

#### Neuropsychiatric Inventory (Cummings et al. 1994)

Ten behavioral and 2 neurovegetative areas (i.e. domains) are included in the NPI: delusions, hallucinations, agitation/aggression, depression/dysphoria, anxiety, elation/euphoria, apathy/indifference, disinhibition, irritability/lability, aberrant motor behavior, sleep and nighttime behavior disorders and appetite and eating disorders. An initial question assesses the 10 items and 2 neurovegetative evaluations of the scale. If the answer to the initial question is 'no', no further questions are pursued. If the answer is 'yes', sub questions are asked; ratings of the frequency and severity of the behavior(s) are determined by the caregiver according to the criteria provided with each behavior. Distress induced in the caregiver by each behavior is also rated. Therefore, a total of 3 scores are recorded for each behavior type: frequency, severity, and caregiver distress. A domain score will be computed as the product of the frequency and severity scores are non-missing.

The psychosis domain score will be calculated as the sum of the delusions and hallucinations domain scores. If either domain score is missing, the psychosis domain score will be set to missing.

The 10-item Total score will be calculated as the sum of all individual NPI domain scores, except for the sleep and appetite domains. If any individual domain score is missing, the Total score will be set to missing.

#### Clinical Global Impression of Improvement (Guy, 1976)

The CGI-I is a 7-point scale that requires the clinician to assess how much the patient's illness has improved or worsened relative to baseline (Visit 2). The scale ranges from 1=very much improved to 7=very much worse.

#### Mini-Mental State Examination (Folstein et al., 1975)

The MMSE is a simple, 30-question, pen-and-paper test that evaluates attention, orientation, memory, registration, recall, calculation, language, and the ability to draw a complex polygon. The range for the total MMSE score (i.e. the total number of correctly answered items) is 0 to 30, with lower scores indicating greater impairment. If any individual item is missing, the MMSE score will be set to missing.

#### Unified Parkinson's Disease Rating Scale Part III (Fahn, 1987)

Part III of the UPDRS is an investigator-scored scale used to assess the motor symptoms of patients with Parkinson's disease. The investigator rates the patient on 14 items based on observation or the performance of a task the patient performs (even in the context of any comorbidities) on a 5-point scale.

The scores range from 0 to 4, with higher scores indicate greater impairment. The total UPDRS score will be calculated as the sum of all items. If any individual item is missing, the UPDRS score will be set to missing.

Note that patients who enrolled under protocol MP-101-01(a) were to complete the UPDRS at baseline, at Weeks 2 and 10, the follow-up visit, and (possibly) at the early termination visit. For protocol MP-101-01(b), the Week 2 visit was moved to Week 4. For purposes of analysis, the Week 2 and Week 4 data will be summarized together as "Week 2/4".

#### Zarit Burden Interview-22 (Zarit et al., 1980)

Changes in caregiver burden will be assessed using the Zarit Burden Interview-22 (ZBI-22). The ZBI-22 is a 22-point scale used to assess caregiver burden in the dementia patient population. Each of the 22 items is rated on a scale of 0 to 4, where 0 = never, 1 = rarely, 2 = sometimes, 3 = frequently, 4 = nearly always. The total score of the ZBI-22 is the sum of these 22 items.

#### **Columbia Suicide Severity Rating Scale**

Any occurrence of suicide-related thoughts and behaviors will be assessed using the C-SSRS, a scale that captures the occurrence, severity, and frequency of suicide-related thoughts and behaviors during the corresponding assessment period. The scale includes suggested questions to elicit the type of information needed to determine if a suicide-related thought or behavior occurred.

The first time the scale is administered in this study, the C-SSRS "Lifetime/Recent-Clinical" version will be used, and the findings will constitute the baseline assessment. The "Since Last Visit-Clinical" version will be used for all subsequent assessments. If a suicide-related thought or behavior is identified at any time during the study, a thorough evaluation will be performed by a study physician, and appropriate medical care will be provided. If, based on administration of the C-SSRS, it is determined that suicide-related behaviors have occurred, the additional information will be collected to allow for a more complete assessment of these behaviors.

Only listings will be created from the individual C-SSRS items.

## **3. INTERIM ANALYSES**

An interim analysis of safety and PK data will be performed after approximately 20 patients have completed Visit 5 (Week 4). In order to minimize the operational and statistical bias that result from performing an interim analysis, the interim analysis for this study will be conducted under the auspices of an Assessment Committee (AC). The purpose of the AC is to advise the Sponsor regarding the continuing safety of study participants and the ongoing scientific validity and integrity of the trial.

No statistical tests will be performed on the data from the interim safety/PK analysis, and no adjustments will be made to the final analysis because of the interim safety/PK analysis.

Displays used the in the interim safety/PK analysis will be a subset of those used in the final analysis (except for one PK figure), so that the description of the display will be included in this SAP.

A second interim analysis may be performed to evaluate the futility of finding differences in the NPI response rates between treatment groups.

All interim analysis details, including unblinding plans and stopping rules for the futility analysis, will be documented in the AC Charter.

# 4. **PATIENT CHARACTERISTICS**

# 4.1. Patient Disposition

The disposition of all randomized patients will be presented. The number of patients will be presented by population, by randomization strata, and by last scheduled visit previous to withdrawal. In addition, the reason for study discontinuation will be tabulated for the overall population and by treatment group using the list of reasons provided in the eCRF.

# 4.2. Protocol Violations

A list of protocol violations that could potentially impact the analysis of the study will be determined during the conduct of the study by study team members who are blinded to study treatment being received. These will be presented in a listing.

# 4.3. Demographics and Baseline Assessments

Patient's baseline age, gender, race, height, body weight, body mass index, MMSE score, other baseline efficacy measures, initial disease history and pre-existing conditions, and eGFR values will be summarized using descriptive statistics by treatment arm and overall. These summaries will be based on the Safety population. Patients who are missing measurements of the baseline variable being analyzed will not be included in the summary for that variable.

A summary will be made by age categorized as 50-64, 65-84, and 85 or older.

Results of examinations of Hepatitis B surface antigen, Hepatitis C antibody, and HIV results, and substance use will be included in listings.

Patient height and weight will be collected prior to randomization. Both variables will be reported in metric units (height in cm and weight in kg) and will be summarized as continuous variables along with Body Mass Index (in  $kg/m^2$ ).

No statistical testing will be performed for comparisons of baseline characteristics.

# 4.4. Concomitant Medications

Concomitant medications will be defined as medications taken on or after the date of the first dose of study treatment. This includes all medications initially taken prior to the date of first dose of study treatment but with a stop date that is either missing or after the date of first dose of study treatment. Those medications where the stop date is documented as prior to the date of first dose of study treatment will be classified as prior medications. The prior medications will not be included in any summary reports.

The percent of patients who receive each concomitant medication, based on the WHODD preferred drug name, will be tabulated. By-patient listings of all concomitant medications that includes WHODD preferred drug names will be prepared.

# 5. EFFICACY ANALYSES

## 5.1. Primary Analysis

The primary analysis of the NPI response rate will use a one-sided Fisher's exact test with a 5% type 1 error rate. The lower 95% confidence limit of the difference in NPI response rates (MP-101 minus Placebo) will be calculated using an exact unconditional confidence interval.

#### **Supporting Analyses**

A supporting analysis of the NPI response endpoint will be performed using a Cochran-Mantel-Haenszel test, stratifying by the randomization strata.

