7.2. Method of Treatment Assignment

Patients who meet all criteria for enrollment will be randomized in a 1:1 ratio (MP-101:placebo) to double-blind treatment at Visit 2 (Week 0). Assignment to treatment arms will be determined by a computer-generated random sequence using an interactive web-response system (IWRS). The IWRS will be used to assign blister packs containing double-blind investigational product to each patient. Blister packs will be dispensed at Visits 2, 4, 5, and 6, (Weeks 0, 2, 4, and 6, respectively). During the patient's visit, the site will access the IWRS for the correct blister pack numbers to dispense.

Randomization will be stratified by baseline MMSE score and eGFR value:

- MMSE < 16 or MMSE > 16
- eGFR <60 or eGFR > 60

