10.3.3. Efficacy Analyses

10.3.3.1. Primary Analyses

The primary objective of this study will be assessed in the Evaluable population by analyzing NPI response rates. Response will be defined using two NPI endpoints: 1) the psychosis domain score, calculated as the sum of the delusions and hallucinations domain scores, and 2) the aggression/agitation domain score. Each domain score is the product of the severity and frequency ratings.

A patient with a 30% improvement from baseline on a subscale will be considered a responder for that subscale. At baseline, patients will be given a diagnosis of psychosis and/or agitation/aggression. A patient with a psychosis diagnosis will be considered an overall responder with a response on the psychosis subscale, a patient with a diagnosis of aggression/agitation will be considered an overall responder with a response on the aggression/agitation subscale, and a patient with both diagnoses will be considered an overall responder with a response on either subscale.

The primary analysis will use a one-sided Fisher's exact test with a 5% type 1 error rate.

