## **1.4.** Sample Size Determination

Approximately 100 patients will be enrolled to enable approximately 80 evaluable patients to complete the study through at least Visit 5 (Week 4).

The primary analysis will use a one-sided Fisher's exact test with a 5% type 1 error rate.

If the NPI response rate in MP-101 treated patients is 30% greater than in placebo treated patients (65% vs 35%), with 40 evaluable patients per treatment group there is at least an 80% chance (i.e. Power) that MP-101 will demonstrate superiority to placebo.

The sample size was calculated assuming an expected 20% drop-out rate of patients in each arm prior to Week 4, so that 100 patients are planned to be enrolled to arrive at 40 patients/arm (N=80) in the Evaluable population.

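### Baseline diagnosis group predicts NPI response by construction, but the only planned adjusted analysis stratifies by MMSE and eGFR alone

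*SAP*

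**What the plan says.** - **Responder rule.** Protocol 10.3.3.1 judges a single-diagnosis patient on the matching subscale. For dual diagnosis it says "a patient with both diagnoses will be considered an overall responder with a response on either subscale". SAP 1.3, as printed, repeats the agitation/aggression clause at this point and does not mention the alternative subscale. SAP 1.1 gives the SAP precedence over the protocol's statistical sections.
- **Randomisation.** Protocol 7.2: "Randomization will be stratified by baseline MMSE score and eGFR value". SAP 2.2 agrees.
- **Primary test.** SAP 5.1: "The primary analysis of the NPI response rate will use a one-sided Fisher's exact test with a 5% type 1 error rate". It is unadjusted.
- **Adjusted analysis.** The one supporting analysis in SAP 5.1 is "performed using a Cochran-Mantel-Haenszel test, stratifying by the randomization strata". SAP 2.10 names as covariates the baseline value of the endpoint and the four MMSE-by-eGFR strata, not diagnosis.
- **Use of diagnosis.** SAP 2.11 derives diagnosis from baseline NPI scores and uses it only for subgroup analyses, with the remark "A patient can be in both subgroups".

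**The concern.** A dual-diagnosis patient has two ways to succeed and a single-diagnosis patient has one. Unless the two subscale responses always coincide, or dual patients respond less often on each scale, the dual group will have the higher response rate. The endpoint definition creates this predictor. It is known before the first dose and is already derived for SAP 2.11.

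With about 40 evaluable patients per arm and no balancing on diagnosis, the dual share will differ between arms by chance, and part of the observed difference will reflect that. An adjusted supporting analysis should show whether the primary result survives imbalance in known predictors, and MMSE and eGFR strata cannot do that for diagnosis. The planned subgroups do not fill the gap, because dual patients appear in both and are never shown separately. If an imbalance occurs, an analysis by diagnosis will be asked for, and one added after unblinding will look selective.

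**Working it through.** **Inputs from the documents.** 65% v 35% response, 40 evaluable per arm, one-sided 5% Fisher test (SAP 1.4 and 5.1), 1:1 allocation (protocol 7.2).

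**Inputs assumed.** Dual share *f*; correlation *ρ* between the two subscale responses in a dual patient; the same response probability *a* on each scale for single and dual patients. The documents give none of these.

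**1. The plan's own figure.** SAP 1.4 states that "with 40 evaluable patients per treatment group there is at least an 80% chance (i.e. Power) that MP-101 will demonstrate superiority to placebo". Exact enumeration of the Fisher test at 40 v 40 gives 79.5%, marginally short of 80%. The continuity-corrected normal formula gives 40 per arm, as planned. With 20% drop-out, 80/0.8 = 100 enrolled, also as planned.

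**2. Response by diagnosis.** P(dual) = 2a − a² − ρa(1 − a), with (1 − f)a + f·P(dual) set to 0.35 for placebo and 0.65 for MP-101.

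| f | ρ | Placebo single / dual | MP-101 single / dual |
|---|---|---|---|
| 1/3 | 0 | 28.2% / 48.5% | 56.8% / 81.4% |
| 1/2 | 0 | 25.5% / 44.5% | 52.5% / 77.5% |
| 1/2 | 0.3 | 28.0% / 42.0% | 56.4% / 73.6% |
| 1/2 | 0.6 | 30.7% / 39.3% | 60.2% / 69.8% |

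**3. Chance imbalance.** The SD of the difference in dual share is √(2f(1 − f)/40): 8.9 points at f = 0.2, 10.5 at 1/3 and 11.2 at 1/2.

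**4. Shift in the response difference.** SD × mean dual-minus-single gap over the two arms. At f = 1/3 and ρ = 0 the gaps are 48.5 − 28.2 = 20.3 and 81.4 − 56.8 = 24.6, mean 22.5. Then 0.105 × 22.5 = 2.4 points at one SD and 4.7 at two. At the same share the one-SD shift is 1.7 points for ρ = 0.3 and 1.0 for ρ = 0.6. Over shares of 20-50% and ρ of 0-0.6 it runs from 0.8 to 2.5 points. For scale, the standard error of the difference is √(2 × 0.65 × 0.35/40) = 10.7 points.

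**5. Conditional one-sided type I error of the CMH test** (simulation, f = 1/2, no drug effect, four equal MMSE/eGFR strata with no effect on response):

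| Dual patients, MP-101 v placebo | ρ | Planned strata | Diagnosis strata |
|---|---|---|---|
| 22 v 18 | 0 | 6.4% | 5.1% |
| 22 v 18 | 0.3 | 6.3% | 5.2% |
| 22 v 18 | 0.6 | 5.6% | 4.9% |
| 24 v 16 | 0 | 9.5% | 5.4% |
| 24 v 16 | 0.3 | 8.1% | 5.3% |
| 24 v 16 | 0.6 | 6.7% | 4.8% |

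The 24 v 16 split is 8/40 = 20 points, or 20/11.2 = 1.8 SD. Taking shares from one-third to one-half at about two SD, the planned test runs at about 6.5-9.6%.

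**6. Averaged over chance imbalance.** Type I error is about 5% under either stratification. At f = 1/2, power is 85.6% planned v 87.6% by diagnosis alone (ρ = 0), and 86.2% v 87.3% (ρ = 0.3). Across the cases run the gain is 0-2 points. Crossing single/dual with all four strata (8 cells) changes power by about +0.6 to −1 point.

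**7. The primary Fisher test.** Its type I error is about 3% averaged over imbalance, about 2.7% when the arms are balanced, and at most about 6.2% at two SD (f = 0.3, ρ = 0). Conditional power at 24 v 16 in either direction (ρ = 0) is about 90% or 66%, against 80% when balanced.

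**The case against.** - **Only a supporting analysis changes.** The unadjusted Fisher test decides the trial, and new CMH strata cannot alter its result. This stands.
- **There is no bias.** A reader might infer that chance imbalance invalidates the primary result. It does not: randomisation keeps the test valid on average, and the inflation above is conditional on a particular imbalance. Matching the adjusted analysis to the randomisation strata is a standard choice.
- **The premise is unsettled.** The second route to response is protocol wording. Read literally, SAP 1.3 removes it, and the SAP takes precedence. The printed repetition may be a drafting or text-extraction error, so it does not show a deliberate change of rule. Even under the literal reading, diagnosis groups would be judged on different subscales and adjustment would remain sensible, but the sizes above would not apply.
- **Zero correlation is the upper end of the range considered.** Positive correlation shrinks the shift, and equal per-scale response in single and dual patients is unsupported by the documents. This stands, which is why a range is given.
- **Adding diagnosis to the existing strata need not help.** This stands: full crossing brings little or no power gain. Three groups by four strata would leave 80/12, about 7 patients per cell.
- **Some cover exists already.** SAP 2.11 plans subgroup analyses, SAP 4.3 summarises baseline efficacy measures by arm, Core Total response applies one rule to all patients, and SAP 1.1 allows extra supportive analyses without amendment. These help to show an imbalance, but none adjusts NPI response for diagnosis.

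**Conclusion.** The point holds as a modest precision and robustness gap. Under the protocol's responder rule, the only adjusted analysis of NPI response omits the baseline predictor that the endpoint definition creates. The effect is small against the planned 30 points: about 0.8-2.5 points per SD of imbalance. It becomes noticeable in the planned CMH test only at about two SD, where the conditional type I error is about 6.5-9.6% and stratifying by diagnosis brings it back to about 5%. The average power gain is 0-2 points.

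These sizes rest on an assumed dual share (20-50%; one-third to one-half for the error rates), a correlation of 0-0.6, equal per-scale response in single and dual patients, and the protocol's wording. The documents do not support the stronger reading that the primary analysis is biased or that its error rate is wrong on average. The case for acting is that the variable is already defined and the change is nearly free.

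**What to change.** In SAP 5.1:

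1. Keep the primary Fisher test and the planned CMH analysis as they are.
2. Pre-specify one additional supporting analysis of NPI response: either a CMH test stratified by diagnosis group alone (single v dual, or the three exclusive groups built from the SAP 2.11 baseline definitions), or a model with main effects for diagnosis group and the randomisation strata. Choose one before unblinding.
3. Report the adjusted difference with its confidence limit, and tabulate diagnosis group by arm.
4. Do not cross diagnosis with all four strata (8 to 12 cells for about 80 patients), and do not include a fallback that depends on how sparse the cells turn out to be.
5. Reconcile the dual-diagnosis responder wording in SAP 1.3 with protocol 10.3.3.1.

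The cost is one derived variable, a few sentences in the SAP and one more supporting analysis to report. No new data are needed, and randomisation and sample size do not change.
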